STUDY PROTOCOL AND STATISTICAL ANALYSIS PLAN

Study title: A Randomized Controlled Trial to Investigate the Cognitive, Mood, Anti-inflammatory and Metabolic Effects of Chronic Oyster Mushroom Intervention in Older Adults.

Acronym: OYSCOG

Date: 01 October 2023

The Pleurotus oyster species is a common edible mushroom rich in ergothioneine, a bioactive compound with known neurocognitive benefits. The aim of the OYSCOG is to investigate the chronic effect (12-weeks) of the equivalent 1 portion of ergothioneine-rich Pleurotus oyster mushrooms (in dried powdered form) on cognition and mood, with examination of the potential inflammatory, metabolic, and neurological related mechanisms that may underlie these effects.

1. Sample Size Calculation

A power calculation based on similar research investigating the chronic benefits of other mushroom interventions on cognitive function suggests that 72 participants should give sufficient statistical power (with $\alpha=0.05$, $\beta=0.80$, Cohen's $d=0.60$). This calculation was based on the average Cohen's d value obtained from 7 RCTs examining the effect of Lion's Mane (Mori et al., 2009; Saitsu et al., 2019; Li et al., 2020; Grozier et al., 2022), Reishi mushroom (Tsuk et al., 2017; Wang et al., 2018) or vitamin D enriched mushroom (Zajak et al., 2020) on global cognitive performance.

To allow for a 10% attrition rate, 80 healthy older adults aged 60-80 years old will be recruited primarily from the University of Reading Ageing Research Panel and the local community. Given the parallel design of the RCT, the cohort will be half split to receive either the control intervention ($N=40$) or the oyster mushroom intervention ($N=40$).

2. Recruitment and Screening

Participants will be initially recruited using opportunity sampling. The study will be advertised via email and posters will be placed around public areas (eg university area, sports hall, library, churches, parkruns, GP practices). Furthermore, participants will be recruited from the Age UK Berkshire and the local community.

Before interested participants are enrolled in our study, they will be invited to attend a familiarisation session to our unit, to determine if they meet the eligibility criteria and they will be given an opportunity to become familiar with the cognitive task battery to reduce the influence of practice effects. Participants will be compensated with £100 for completing all study visits.

3. Inclusion/Exclusion criteria

Inclusion criteria

- Aged between 60-80 years old
- Have normal vision and hearing
- Have healthy status
- Have normal body mass index (cutoff: $BMI \leq 30$)

Exclusion criteria

- Smokers
- Vegans/vegetarians
- Being diagnosed with psychiatric/neurological condition (eg., stroke, schizophrenia, depression, cognitive impairment, dementia)
- Being diagnosed with a learning/behavioural disorder (eg., dyslexia, autism, ADHD)
- Being diagnosed with a metabolic disease (eg., type I/II diabetes and cardiovascular disease), or suffer from unmedicated hypertension or thrombosis related disorders

- Being anaemic
- Taking disease medication such as anticoagulants, antiplatelet medication, dementia medication, antidepressants, antiepileptic medication, or thyroid medication
- Currently taking regular vitamin supplements (including prebiotics/probiotics)
- Have food allergies
- Having a difficulty in completing computer-based cognitive tasks

4. Randomisation Process

The study will be double blinded since neither the participants nor the researcher will know which intervention meal participants are receiving until the study is over. To achieve this, the Latin Square design will be followed, by using blocked randomisation with random permuted blocks of two. Another individual not being involved in this study, will assign a code to the placebo and mushroom intervention and these will be kept in a sealed envelope, concealed to the researcher enrolling and assessing participants.

5. OYSCOG study Protocol

During this 2-arm parallel double-blind study, participants will attend the University of Reading, Psychology department on three separate occasions; a) a familiarisation visit; b) a baseline visit, a week after the familiarisation visit and c) a post-visit, 12-weeks after the baseline visit.

In the pre-screening phase, the participants interested in our study will be sent a link to REDCap containing online versions of a Health and Lifestyle Questionnaire and the Epic Norfolk Food Frequency Questionnaire (FFQ). Then, participants, will be contacted to attend a 3-hour familiarisation session at our department, during which the participant's weight, height and blood pressure will be checked, along with a finger-prick, to ensure that the participants are not anaemic. Furthermore, participants will complete the Raven's Progressive Matrices (RPM) measure of fluid intelligence and will perform the cognitive battery tasks twice to control for practice effects in the run up to the test session days. Also, the head and cap size measurements will be taken in a subset of participants (N=20 from each experimental group) that agreed to undertake the EEG at the testing visits.

At the end of the familiarisation visit, participants will be allocated to one of the treatment groups and they will receive a 12-week supply of the intervention powder in sachets. After the familiarisation visit, participants will be asked to follow a low flavonoid diet for 24-hours in advance of the two testing days. In both the baseline and post-visit testing sessions, participants will be instructed to perform several cognitive and mood related tasks. In addition to the behavioural tests, blood pressure, heart rate and body weight will be measured, and electroencephalogram (EEG) measurements will be recorded in a subset of participants using electrodes placed on the scalp for detecting electrical brain activity. Finally at the end of each testing visit, a blood sample will be taken. Each test visit will last approximately 2 hours. **Figure 1** summarises the OYSCOG testing protocol.

[figure not shown]

Figure 1: Study design of the parallel 2-arm OYSCOG RCT, investigating the chronic effects of ergothioneine-rich Pleurotus mushrooms on cognition, cognition, inflammation, and metabolism.

The cognitive-mood battery used will contain the following tasks:

- Positive and Negative Affect Schedule (PANAS-X)- In this mood task, participants are asked to rate their emotion on a 5-point Likert scale, in response to negative emotions (e.g., guilt, fear), positive emotions (e.g., attentiveness, joy) and other affect states (e.g., surprise, shyness).
- Depression, Anxiety and Stress Scale - 21 items (DASS-21)- This 21-item measure assesses symptoms of depression, anxiety and stress. Each item is scored from 0-3 where higher scores indicate higher levels of distress in anxiety (scores range from 0 to >20), depression (0 to >28) or stress (0 to >34).
- Rey Auditory Verbal Learning Task (RAVLT)- This episodic memory task consists of 5 consecutive free recalls of the same 15 nouns presented as an auditory list (list A), followed by recall of a further 15 nouns presented as an interference list (list B) which is recalled only once. List A is subsequently recalled straight after list B and then again after a longer delay of around 30 minutes.
- Task Switching Task (TST) - In this executive function task, participants view 8 spaced radii of a circle above and below a bold line and a stimulus digit selected from 1-9 (except 5) appears clockwise in each segment, either above or below the bold line. Depending on the stimulus position in the segments, participants perform different tasks with each being switched every 4 trials.
- Corsi block tapping task (CBTT)- In this spatial working memory task, participants are shown 9 arranged blocks positioned on a computer screen and are asked to reproduce a given sequence by clicking on the blocks (using the mouse) in the same sequence as they see them.
- Simple and complex finger tapping task (SFT & CFT)- In this psychomotor function task, participants tap on a key as quickly as possible with the index finger of their dominant hand for 1 minute. They then tap out a specific sequence using 4 fingers, again for 1 minute.
- RAVLT word recognition- In this delayed memory task, participants are shown a sequential list of 50 nouns containing the words from lists A and B from the previously

described RAVLT task plus 20 additional words not previously heard, and are asked to indicate those from list A.

•N-back- In this working memory and attention task, participants are shown a series of stimuli, and they will have to respond to indicate whether the stimuli match the target presented at the beginning of the task. This task will be performed while also taking EEG measurements (using Brain Products software and 16 active electrodes), to examine changes in brain activity.

• Subjective mental fatigue- At the end of the cognitive battery participants are asked to rate their mental fatigue level on a 9-point Likert scale.

6. Statistical Plan

All statistical analyses will be performed by using SPSS software. Initially, extreme outliers will be identified and excluded using boxplots (using 3*IQR rule), and subjects with missing data will be excluded from analysis. The main analysis will use a mixed ANOVA to investigate a) the main effect of time (within subject factor, baseline vs 12-weeks), b) the main effect of intervention (between subject factor, placebo vs oyster mushroom group) and c) the intervention*time interaction. For the outcome measures that show significant changes at baseline, a 1-way ANOVA will be applied by treating the baseline scores as a covariate to examine the main effect of intervention. In all analyses, a Bonferroni correction will be examined for post-hoc pairwise comparisons regardless of the significance of the overall F test statistic. Significant comparisons will be reported (*p<0.05, **p<0.01, ***p<0.001).

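### The inputs in Section 1 do not establish 80% power at 72 participants for the two-sided analysis in Section 6: the matching two-sample t test is one-sided, and the two-sided figure is 71%

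*Combined protocol and SAP*

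**What the plan says.** Section 1 (Sample Size Calculation) states that the calculation "suggests that 72 participants should give sufficient statistical power", with α = 0.05, β = 0.80 and Cohen's d = 0.60. The 0.60 is the average "d value obtained from 7 RCTs examining the effect of" other mushroom products on overall cognition. The number is then raised for dropout: "To allow for a 10% attrition rate, 80 healthy older adults" will be recruited, 40 per arm. Section 1 does not name the test, the number of sides, the standard deviation on which d is measured, or a correlation between baseline and 12 weeks.

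Section 6 (Statistical Plan) sets the analysis. "The main analysis will use a mixed ANOVA to investigate" time, intervention and their interaction. A baseline-adjusted analysis is planned only for some outcomes: "For the outcome measures that show significant changes at baseline", "a 1-way ANOVA will be applied by treating the baseline scores as a covariate". In addition, "a Bonferroni correction will be examined for post-hoc pairwise comparisons regardless of the significance of the overall F test statistic". No section states a directional hypothesis or a one-sided test.

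**The concern.** Two things stand out. First, β = 0.80 taken literally is a type II error rate of 80%, that is, 20% power. The intended meaning is clearly power 0.80.

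Second, 72 is smaller than the usual two-sided answer for d = 0.60 at 80% power. An F test with one numerator degree of freedom is equivalent to a two-sided t test, so a sample size that rests on a one-sided test would not fit Section 6.

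The calculation is the only justification given for 72 completers and 80 recruits. If the stated 80% does not belong to the test that will be run, a reader cannot judge how informative a null result is.

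**Working it through.** **Inputs.** From Section 1: α = 0.05, power 0.80 (reading β = 0.80 as power), d = 0.60, equal arms, 72 before attrition, 10% attrition. From Section 6: two groups, two visits, mixed ANOVA. The baseline-to-12-week correlation r is not in the plan. It is varied below as an assumption.

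**Method.** Two-sample t test with n per arm, 2n − 2 degrees of freedom and noncentrality d√(n/2). Power comes from the noncentral t distribution.

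**1. Reproducing 72.** At n = 36 the noncentrality is 0.60 × √18 = 2.546.
- One-sided 0.05: n = 36 gives 80.9% and n = 35 gives 79.96%. The minimum total is therefore exactly 72.
- Attrition: 72/0.9 = 80, as the plan says.

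**2. The same comparison, two-sided 0.05.**

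| Per arm | Total | Power |
|---|---|---|
| 36 | 72 | 0.709 |
| 40 | 80 | 0.75495 |
| 44 | 88 | 0.795 |
| 45 | 90 | 0.804 |

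So 80% needs 90 completers, which is 90/0.9 = 100 recruits. At 36 per arm the difference detectable with 80% power is d = 0.67. A normal approximation gives 88 completers, and 72% power at 72, so the result does not hinge on the formula.

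**3. The intervention-by-time interaction.** With two groups and two visits this is a two-sample t test on change from baseline. Two scales for d are possible.
- *d on the change-score SD.* The effective d is 0.60 whatever r is, so step 2 applies: 71% at 72.
- *d on the raw-score SD.* The SD of change is √(2(1 − r)) raw SDs, so the effective d is 0.60/√(2(1 − r)). At 36 per arm:

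| Assumed r | Effective d | Power at 72 |
|---|---|---|
| 0.3 | 0.60/√1.4 = 0.507 | 56% |
| 0.5 | 0.60/√1.0 = 0.600 | 71% |
| 0.6 | 0.60/√0.8 = 0.671 | 80% |
| 0.7 | 0.60/√0.6 = 0.775 | 90% |

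The 80% line is crossed at r of about 0.60. At r = 0.6 the minimum total is also 72.

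**4. Baseline-adjusted analysis.** With d on the raw-score SD the effective d is 0.60/√(1 − r²), and 80% at 72 needs r of about 0.44 or more. Section 6 reserves this analysis for outcomes that differ at baseline, so it is not the basis for the main test as written.

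**The case against.** The strongest reply is that 72 is a correct answer to a recognisable question. It is the exact one-sided result, and the attrition step is right. The plan states no two-sided α either, and a two-visit analysis can gain power from the correlation between visits. Much of this stands. A reader might infer that 72 is a miscalculation, or that the trial certainly has less than 80% power. The documents support neither: power for the interaction could lie below or above 80%, and the 90 and 71% are one point in that range. Nor do the documents show that a one-sided test was used, because the raw-SD interaction at r = 0.6 also gives 72.

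Another reply is that repeated-measures power software can ask for far fewer people. With f = 0.30 (half of d) entered as the interaction effect under a noncentrality of 2Nf²/(1 − r), 46 suffice at r = 0 and 24 at r = 0.5. Power at 72 is at least 94% for any r of 0 or more, so not every two-sided route depends on a particular r. But that convention implies a larger effect. Setting 2f²/(1 − r) = 0.18/(1 − r) equal to δ²/(8(1 − r)) gives δ² = 1.44, so the difference in change is δ = 1.2 raw SDs, twice the stated 0.60. It does not yield 72 either.

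A between-group test averaged over both visits also reaches 80% at 72 when r is about 0.6 or less, if d = 0.60 holds at both visits. Randomisation makes an equal difference at baseline implausible. However, sachets are handed out at the familiarisation visit, a week before baseline, and the documents do not say when intake begins, so this is not strictly excluded.

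Finally, a reader might want to add a power loss for the Bonferroni comparisons. Section 6 does not give the number of comparisons, and Section 1 does not tie its power to them, so no figure is supportable.

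**Conclusion.** The concern holds in this form: the stated inputs do not establish 80% power for the planned two-sided analysis. β = 0.80 is mislabelled. As a plain two-sample t test, 72 is reproduced only one-sided, which does not match the non-directional tests in Section 6. Two-sided, the power is 71% at 72 completers and 75% at 80 for an unadjusted 12-week difference, or for a difference in change on the change-score SD, of d = 0.60. Two-sided 80% at 72 can be reached only with a correlation or an effect-size convention that the plan does not state.

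The two-sided figures rest on reading β = 0.80 as power and on equal arms; the 56% to 90% range for the interaction also rests on assumed values of r. The actual power cannot be determined from the documents. This should be fixed, but it does not call the sample size itself into question.

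**What to change.** Keep 80 recruits and rewrite Section 1:
- Replace β = 0.80 with power 0.80 (β = 0.20) as the target, and state that α = 0.05 is two-sided.
- Name the intervention-by-time interaction as the powered test and state the SD on which d is measured.
- If d is on the change-score SD, say that 36 completers per group give 71% power for d = 0.60 and 80% power for d = 0.67.
- If d is on the raw-score SD, give the power at 72 over a range of r (56%, 71%, 80% and 90% at r = 0.3, 0.5, 0.6 and 0.7). Claim 80% only for an r taken from a cited source, not one chosen to recover 72.

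The cost is rewording one section and checking the seven cited trials for the scale of d and a usable r. No extra recruitment is needed. The downside is that the stated power may become less favourable.

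### Blocks of two with one code per arm make every second code predictable if the enrolling researcher can see the codes, and the plan describes no safeguard against that

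*Combined protocol and SAP*

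**What the plan says.** Section 1 sets two equal arms: "the cohort will be half split to receive either the control intervention" or the mushroom intervention, 40 each. Section 4 specifies "blocked randomisation with random permuted blocks of two" and, in the same sentence, calls the scheme a Latin Square.

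On coding, section 4 says: "Another individual not being involved in this study, will assign a code to the placebo and mushroom intervention". It continues: "these will be kept in a sealed envelope, concealed to the researcher enrolling and assessing participants". The blinding statement is that "neither the participants nor the researcher will know which intervention meal participants are receiving until the study is over". That sentence concerns the identity of the treatment; it does not say whether the code label is hidden.

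Section 2 places the eligibility decision at the familiarisation session. Section 5 has Raven's matrices and two runs of the cognitive battery at that visit, and then: "At the end of the familiarisation visit, participants will be allocated to one of the treatment groups". The sachets are supplied at the same point. Section 3 includes two criteria with no definition or threshold: healthy status, and "Having a difficulty in completing computer-based cognitive tasks".

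The document does not mention varied or withheld block sizes, several codes per arm, participant-level kit numbers, sequentially numbered envelopes, central allocation or a separate dispenser. It also does not say who hands over the sachets or what is printed on them.

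**The concern.** A decision to enrol should not be open to influence by the allocation that comes next. With two arms and blocks of two, each block is AB or BA, so anyone who has seen the first code of a block knows the second. As described, the envelope appears to guard the key (which code is mushroom) and not the order of the codes.

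Section 4 speaks of one researcher who both enrols and assesses. That person may have watched a candidate's cognitive performance shortly before settling a loosely worded criterion. If the next code is known at that moment, a candidate could be accepted, deferred or excluded with the code in mind, even unconsciously.

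The second exposure is the shared code. Because each code covers a whole arm, one unblinding or one correct guess would reveal the arm of every participant whose code is known. Both the baseline and the 12-week assessments come after allocation, so both would then be open to unblinded assessment.

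**Working it through.** **Inputs from the plan.** 72 evaluable participants and 10% attrition (section 1); two arms, 1:1; fixed blocks of two (section 4).

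**The plan's own figure.** 72 / (1 − 0.10) = 80, which is 40 + 40, or 40 blocks of two. This reproduces. The plan gives no figure for predictability.

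**Predictability, if codes are visible and the scheme is known.** For a fixed block of size 2m:
- share of allocations certain in advance = 1/(m + 1);
- expected correct guesses per block, always guessing the code with more places left = m + (4^m / C(2m, m) − 1)/2.

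For m = 1: certain share = 1/2, or 40 of 80; correct guesses = 1 + (4/2 − 1)/2 = 1.5 of 2, which is 75%, or 60 of 80.

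**Bias in follow-up level.** Assumption: the enrolling researcher shifts the prognosis of each selected participant by s = 0.2 SD, up or down according to the predicted arm. The documents give no such figure. With c the proportion guessed correctly, right minus wrong guesses over 80 participants is 80(2c − 1). Dividing by 40 per arm gives bias = 2s(2c − 1). For blocks of two: 2 × 0.2 × (1.5 − 1) = 0.20 SD. Put another way, half of each arm is predictable, so the arm means move by 0.10 SD in opposite directions.

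| Scheme, codes visible | Certain in advance | Guessed correctly | Bias, key known from the start |
|---|---|---|---|
| Simple randomisation | 0% | 50% | 0 |
| Blocks of 2 (plan) | 50% (40 of 80) | 75.0% | 0.20 SD |
| Fixed blocks of 4 | 33.3% (26.7 of 80) | 70.8% | 0.17 SD |
| Fixed blocks of 6 | 25.0% (20 of 80) | 68.3% | 0.15 SD |
| Random mix of 4 and 6 (simulated) | about 5.5% | about 69.1% | 0.15 SD |

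The last row assumes the guesser knows that the sizes are 4 and 6 but not their order.

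**When the key is guessed.** Selection by code without a view on which code is mushroom has no expected direction. If the key is correctly guessed only after k participants, the bias is 0.20 × (80 − k)/80:
- k = 0: 0.20 SD
- k = 40: 0.10 SD
- k = 60: 0.05 SD
- never: 0

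A wrong guess gives the same size in the opposite direction. The figures scale with s: at k = 0, s = 0.1 gives 0.10 SD and s = 0.3 gives 0.30 SD.

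**What the planned analysis does with it.** Section 6 tests the intervention-by-time interaction in a mixed ANOVA. A shift L in level that is present at both visits gives (effect + L) − L = effect, so it drops out. It stays in the main effect of intervention, which section 6 also lists and which averages the two visits. Selection on expected change, or assessment influenced by knowledge of the arm, does not drop out of the interaction.

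**The case against.** The strongest reply is that the plan never says the researcher sees a code. Section 4 can be read to mean that the codes themselves, and not only their meaning, are concealed from the person who enrols and assesses; section 5 says only that participants receive a supply. On that reading prediction fails. This stands, and it is why the point is conditional. The plan nevertheless leaves open how an enrolling researcher would be kept from seeing the labels.

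Second, a predicted code is not a predicted treatment. A reader might infer a bias of 0.20 SD, one third of the planned d of 0.60. The documents do not support that as an estimate. It takes an assumed selection shift, supposes the key is known from the first participant, and describes a difference in level that the interaction would largely remove. A cue such as a remark on taste could come only after someone had started the powder, and the next scheduled contacts are one week and about 13 weeks after allocation. Such a remark supports a guess; it does not prove the key.

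Third, most criteria are objective (age, BMI, smoking, diagnoses, medication, the finger-prick test for anaemia), and health and lifestyle are pre-screened online. This narrows the room for discretion but leaves the two undefined criteria.

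Fourth, block size is not the main driver. With visible codes, mixed blocks of 4 and 6 still allow about 69% correct guesses. This also stands, and it determines which part of the remedy matters most.

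**Conclusion.** This is a weakness in allocation concealment as written, worth correcting (should-fix, medium confidence). Given one visible code per arm, the arithmetic is certain: 40 of 80 codes are determined in advance and 75% are guessable. The conclusion rests on two inferences: that each arm has a single code, which is the natural reading, and that the enrolling researcher can see it, which the plan neither states nor prevents.

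The consequence for the result is uncertain. Under the assumed 0.2 SD shift, the bias in follow-up level lies between 0 and 0.20 SD depending on when, if ever, the key is guessed, and a stable shift largely cancels from the interaction. A reader might go further and conclude that the researcher does know every second allocation, or that enrolment will be biased. The documents show neither.

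**What to change.** - The independent person already named in section 4 prepares a list of 80 unique kit numbers. Sachets carry only the kit number, with no code shared across an arm. This is the essential part, because it removes the sequence from view and limits any single unblinding to one participant.
- The list uses randomly mixed larger blocks, for example of 4 and 6, with the sizes withheld from the enrolling researcher. Eight blocks of each size would keep the total (8 × 4 + 8 × 6 = 80) and the 40:40 split.
- The eligibility decision is recorded before the next kit is assigned.
- Section 4 states who holds the list and who hands over the sachets. If individual labels are already intended, it should say so.
- The Latin Square reference is removed; it describes no allocation mechanism for a two-arm parallel trial and adds nothing to concealment.

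Cost: one new list and slightly more labelling work, with no extra staff or visits. If recruitment stops part-way through a block, the arms could differ by up to 3 participants.

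### Cognitive scores obtainable before allocation are left out of the analysis; an ANCOVA on baseline plus the second familiarisation run would be more precise than the planned change-score test

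*Combined protocol and SAP*

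**What the plan says.** Section 5 (OYSCOG study Protocol) has participants attend a familiarisation visit, then "a baseline visit, a week after the familiarisation visit", then a visit 12 weeks after baseline. At familiarisation they complete the Raven's Progressive Matrices ("RPM) measure of fluid intelligence and will perform the cognitive battery tasks twice to control for practice effects"). Both measures precede randomisation: "At the end of the familiarisation visit, participants will be allocated to one of the treatment groups".

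Section 6 (Statistical Plan) names neither the Raven's nor the familiarisation runs. The main analysis is a mixed ANOVA with time (baseline, 12 weeks), intervention and their interaction, and no covariate. For outcomes that show what the plan calls significant changes at baseline, which I read as differences between arms, "a 1-way ANOVA will be applied by treating the baseline scores as a covariate to examine the main effect of intervention". Subjects with missing data are excluded.

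Section 1 (Sample Size Calculation) states that "72 participants should give sufficient statistical power" at Cohen's d 0.60. It recruits 80 to allow for 10% attrition, split equally between arms, and uses no covariate.

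**The concern.** One sitting of a cognitive task measures ability with error. A second pre-allocation score on the same task, about a week earlier, can absorb more of the between-person variation in the 12-week score than the baseline visit alone, and treatment cannot have affected it.

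The planned test does not exploit even the baseline score fully. With two time points, the intervention-by-time test is a two-sample comparison of change scores. That fixes the coefficient on baseline at 1, where ANCOVA would estimate it. ANCOVA is used only for outcomes flagged at baseline, so the model also varies between outcomes according to the data.

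What is at stake is precision, not bias: a trial planned for 72 completers would report wider intervals than its own measurements allow.

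**Working it through.** **The plan's own figure.** A two-sample t-test with d = 0.60, alpha 0.05 and power 0.80 (Section 1 prints 0.80 as beta; I read it as power) gives 36 per arm, 72 in total, if one-sided (power 80.9%). Attrition: 72/0.9 = 80. Two-sided, the same test needs 45 per arm (90), and 72 gives 70.9%. Section 1 does not state sidedness; that is a separate point. The power figures below are two-sided.

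**Inputs.** N = 72 is from Section 1. The rest are assumptions, because the documents give no correlations:
- r, baseline with 12 weeks: 0.5 to 0.8.
- s, run 2 with 12 weeks, and q, run 2 with baseline. Equal pattern: s = q = r. Closer-to-baseline pattern: q = r + 0.10, s = r − 0.05.
- Equal variances at each visit, set to 1; d = 0.60 on the final-score SD.

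**Residual variances.**
- Planned change-score test: 2(1 − r).
- ANCOVA on baseline: 1 − r².
- ANCOVA on baseline and run 2: 1 − (r² + s² − 2rsq)/(1 − q²). In the equal pattern this is 1 − 2r²/(1 + r).

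Example, r = 0.5. Change score: 2 × 0.5 = 1.000. Baseline ANCOVA: 1 − 0.25 = 0.750. With run 2, equal pattern: 1 − 0.5/1.5 = 0.667. With run 2 closer to baseline (q = 0.60, s = 0.45): 1 − (0.25 + 0.2025 − 0.27)/0.64 = 0.715.

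| r | Change | Baseline ANCOVA | + run 2, equal | + run 2, closer to baseline |
|---|---|---|---|---|
| 0.5 | 1.000 | 0.750 | 0.667 | 0.715 |
| 0.6 | 0.800 | 0.640 | 0.550 | 0.607 |
| 0.7 | 0.600 | 0.510 | 0.424 | 0.488 |
| 0.8 | 0.400 | 0.360 | 0.289 | 0.355 |

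**Full model against the planned test.** For r = 0.5, 0.6, 0.7 and 0.8:
- Equal pattern: reductions of 33%, 31%, 29% and 28%.
- Closer-to-baseline pattern: 29%, 24%, 19% and 11%.

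**Degrees of freedom.** With k covariates the variance of the arm effect is multiplied by 1 + k/(N − k − 3). For k = 2 this is 1 + 2/67 = 1.030; for k = 1 it is 1 + 1/68 = 1.015. Net of the two-covariate cost, the reductions are 26-31% (equal) and about 9-26% (closer to baseline).

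**Where the gain arises.** Baseline ANCOVA alone cuts the change-score variance by 25%, 20%, 15% and 10%. Run 2 on top of it gives:
- Equal pattern: a further 11%, 14%, 17% and 20%; net of its degree of freedom, 10-19%.
- Closer-to-baseline pattern: a further 5%, 5%, 4% and 1%; net, from a 4% gain to a 0.2% loss.

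Moving to ANCOVA is therefore the larger part everywhere except the equal pattern at r = 0.8, where it removes 10 of the 28 percentage points.

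**Power at r = 0.5.** Planned test 70.9%; baseline ANCOVA 82.0%; with run 2, 85.7% (equal) or 83.3% (closer to baseline).

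**Raven's.** Assume it correlates 0.2 to 0.5 with each task score. On top of baseline and run 2 it multiplies the net variance by 0.930 to 1.013.

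**Covariates added to the planned mixed ANOVA instead.** A pre-allocation covariate helps a change-score test only if it predicts change. With run 2 and the Raven's both added, variance is multiplied by 1.030 in the equal pattern and by 0.953 to 1.006 in the other.

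**The case against.** The planned comparison is unbiased without these covariates, so their omission is a choice and not an error. Sections 2 and 5 also give the runs a purpose, namely reducing practice effects, so they are unused only in the analysis. Both points stand.

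A reader might infer more than the documents support:

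- **That the scores already exist for everyone.** No section says that the run scores are recorded. The RAVLT is free recall and has to be scored, and whether its lists differ between sittings is not stated. N-back is described as performed with EEG, which only 20 per group undergo. No familiarisation value is described for blood or EEG outcomes, and for the mood scales it is unclear.
- **That 72 completers become worth 81 to 90.** Those figures are 72/0.889 to 72/0.803. They need run 2 to correlate as well with a visit about 13 weeks later as with one a week later, they ignore degrees of freedom, and their comparator is a baseline-only ANCOVA that is not the planned main analysis.
- **That adding covariates to the existing model is enough.** In the mixed ANOVA they gain almost nothing or lose 3%.
- **That it costs nothing.** Two covariates cost about 3% of variance. Under the complete-case rule, 5% missing covariate values would raise variance by a further 5% (1/0.95 = 1.053).
- **That the baseline score is contaminated by treatment.** Baseline follows allocation and the handing out of the powder, but the documents do not say when intake starts. This makes run 2 a useful safeguard; it does not show that baseline is affected.

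**Conclusion.** The point holds as a precision gain that the plan leaves unused. Both measures precede allocation, Section 6 uses neither, and the planned interaction test is less efficient than an ANCOVA on baseline and run 2 in every case examined. The reduction is about 28-33% with equal correlations and about 11-29% with run 2 closer to baseline, before the 3% cost.

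The firmer part is using ANCOVA for every cognitive outcome. The increment from run 2 is real but uncertain, from about nil to 19% net, and the Raven's adds little once run 2 is in. All of this rests on assumed correlations of 0.5 to 0.8 and equal variances across visits. It applies only to tasks for which a familiarisation score is obtained.

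**What to change.** In Section 6, for each cognitive outcome with a familiarisation score, prespecify as the main analysis an ANCOVA of the 12-week score on arm, baseline-visit score and second familiarisation-run score of the same task. Enter the two scores as separate covariates so that the data set their weights. Use the second run because the first is likely to carry most of the task learning. Drop the rule that makes adjustment depend on a baseline difference. Name the Raven's as an optional further covariate, with the choice fixed before unblinding.

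In Section 5, state that second-run scores are scored and stored, and which tasks they cover; clarify N-back and the mood scales. State that a missing covariate is replaced by its overall mean across arms, so that the complete-case rule removes nobody on that account.

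The cost is SAP wording, the work of scoring and storing run 2, and one degree of freedom per covariate (two in the core model, three with the Raven's). No visit or participant burden is added.
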